### **3.6.4 Visit 2 (V2)**

Visit 2 is conducted at week 8 after the enrollment visit. The investigator will document the disease history since the last visit, including all adverse events, changes in concomitant treatment, and changes in concomitant medications doses, if any.

The investigator will analyze the effectiveness of the therapy according to the patient's BP self-monitoring diary data.

The investigator measures blood pressure and heart rate in a sitting position after 5 minutes of rest. **Two** measurements are done; the average value of the measurements is documented. BP is measured on the same arm during the entire study.

The investigator analyzes the patient's compliance based on the number of returned tablets.

The investigator evaluates response to the treatment (target BP reaching), documents it in source documents and decides on further treatment of the patient. If target BP has not been reached, the patient's investigated product dose is titrated according to the study design. If the target BP has been reached, the patient continues with the current treatment until the next visit.

The investigator will invite the patient to the next visit (visit V3) scheduled for week 24 after the enrollment visit (168 days  $\pm$  5 days after the enrollment visit); the patient will be asked to return the investigated medication blisters (empty, started and not started blisters). The patient will be instructed to start taking the provided product the next day morning, 1 tablet per day. The patient will be instructed to report any adverse events (if applicable) to the investigator.

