### **Treatment regimens**

- **Group 1** patients receive moxonidine with dose titration up to the maximum, then a patient may be switched to the combination therapy, if necessary (step 2 - adding an ACE inhibitor).
- **Group 2** patients receive bisoprolol with dose titration up to the maximum, then a patient may be switched to the combination therapy, if necessary (step 2 - adding an ACE inhibitor).

The investigator will provide a Group 1 patient with moxonidine 0.4 mg in the amount required for 56 days of treatment plus 7 extra days and additionally moxonidine 0.2 mg in an amount required for 42 days of treatment if the dose is titrated up to 0.6 mg/day.

The patient will take the first moxonidine tablet immediately during the visit after all the visit procedures are completed. The patient will be instructed to take 1 tablet of moxonidine 0.4 mg in the morning, daily. The next visit will be scheduled in week 8 after the enrollment visit (in 56 days  $\pm$  5 days after the enrollment visit).

The patient will be asked to bring all the blisters of investigated product (empty, started and not started blisters) to every visit after the study initiation.

The investigator will give the patient blood pressure self-monitoring diary which is to be used by the patient to daily document her BP values and to bring it to every subsequent visit.

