#### 3.8.2 Comparative product

**Name:** Cardioselective beta1 blocker. INN: Bisoprolol.

Produced by Merck KGaA, Germany

**Pharmaceutical form:** film-coated tablets.

One tablet contains bisoprolol hemifumarate and bisoprolol fumarate (2: 1) as active substances 5 mg, and the following excipients: calcium hydrogen phosphate anhydrous - 132 mg; corn starch fine powder - 14.5 mg; colloidal anhydrous silica - 1.5 mg; MCC - 10 mg; crospovidone - 5.5 mg; magnesium stearate - 0.97 mg, film coating: hypromellose 2910/15 - 2.2 mg; macrogol 400 - 0.53 mg; dimethicone 100 - 0.11 mg; iron oxide yellow dye (E172) - 0.02 mg; titanium dioxide (E171) - 0.97 mg.

**Posology and method of administration:** Bisoprolol is taken orally, once a day, regardless of meals.

**Duration of treatment:** Bisoprolol 5 mg is prescribed to postmenopausal patients with hypertension and osteopenia. Subsequently, in patients with no response, the daily dose is titrated up to 7.5 mg every 2 weeks; then perindopril 10 mg may be added to the regimen at week 8, if necessary. Patients should take the medication until study week 48 (V4).

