#### **4.5 Study withdrawal criteria**

A patient may be withdrawn from the study before the treatment is started, if the investigator discovers deviations from any inclusion criteria, exclusion criteria, or criteria for the treatment initiation. Patients who withdrew before the treatment start (i.e., during screening or washout period), will be substituted with new patients.

In the present study, withdrawal from the study will also mean discontinuation of the investigated treatment.

The patient may be withdrawn from the study due to the following reasons:

1. Withdrawal of the informed consent to participate in the study.
2. Low treatment compliance (<80%).
3. Adverse events that in the investigator's opinion make the treatment continuation impossible, dangerous, or inconsistent with best patient interest and safety. A SAE is not necessarily the cause of early patient withdrawal from the study.
4. According to the investigator, continued participation of the patient in the study threatens the patient's safety.
5. It is necessary to administer treatment prohibited by the study protocol.
6. Failure of the investigated treatment (i.e., recurrent rise of blood pressure  $\geq 180/120$  mmHg after previously achieved target BP level).
7. Death of the patient.
8. Sponsor decision.

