## **5 Treatment of patients**

### **5.1 Prescribed treatment**

#### **Treatment assignment at the study visits**

**Washout period** is designed for patients who have already been taking antihypertensive medications. All antihypertensive medications are discontinued 7-10 days prior to the enrollment visit. The patient is asked to refrain from taking these and any other antihypertensive medications during the washout period. The average duration of the washout period is 7 days. The investigator may shorten the duration of the washout period, but it should not be shorter than 6 half-life periods ( $T_{1/2}$ ) of the antihypertensive medications patient was taking.

During the washout period, the patient may be administered with fast-acting agents to relieve hypertensive episodes (at the investigator's discretion – nifedipine, captopril). The period from the last dose of these antihypertensives to the enrollment visit must be at least 6  $T_{1/2}$  of these agents (e.g., 18 hours for nifedipine).

If the above conditions are not met, the patient is withdrawn from the washout period and will not participate in the study. The researcher may at any time terminate the washout period, if the patient does not tolerate it well.

The washout period is not required for patients who were not previously treated with antihypertensives, and patients who were not receiving antihypertensives at the time of the screening. If the patient was treated with any antihypertensives earlier and discontinued the medications **before** the screening, the washout period is not necessary for her, if the period between the last dose of the antihypertensives and the enrollment visit is not shorter than 6  $T_{1/2}$  of these drugs.

**All enrolled patients** are randomized in the two study groups (moxonidine group or bisoprolol group).

**All group 1 patients** are prescribed with moxonidine 0.4 mg monotherapy. At the **V1 enrollment visit**, the patient will be given the medication and will take first dose of moxonidine in the presence of the investigator. Thereafter, patients will take the medication every morning, during the entire study. The medication will be dispensed to a patient at visits V1, V2, V3, and the patient will start taking the drug on her own on the day following the visit. One tablet of the investigated product should be taken daily, in the morning, regardless of meals.

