On 2nd week telephone visit, the investigator evaluates efficacy, safety and tolerability of the investigated treatment. Patients will continue taking moxonidine 0.4 mg QD until next visit V2. If BP control is insufficient, the investigator may increase moxonidine dose to 0.6 mg QD.

On 4th week telephone visit, the investigator evaluates efficacy, safety and tolerability of the investigated treatment. Patients will continue taking moxonidine 0.4 mg (0.6 mg) QD until next visit V2. If BP control is insufficient with moxonidine 0.6 mg QD, the investigator adds perindopril 10 mg QD.

**All group 2 patients** are prescribed with bisoprolol 5 mg monotherapy. At the **V1 enrollment visit**, the patient will be given the medication and will take first dose of bisoprolol in the presence of the investigator. Thereafter, patients will take the medication every morning, during the entire study. The medication will be dispensed to a patient at visits V1, V2, V3, and the patient will start taking the drug on her own on the day following the visit. One tablet of the investigated product should be taken daily, in the morning, regardless of meals.

On 2nd week telephone visit, the investigator evaluates efficacy, safety and tolerability of the investigated treatment. Patients will continue to take bisoprolol 5 mg until visit V2. If BP control is insufficient, the investigator will increase bisoprolol dose to 7.5 mg QD.

On 4th week telephone visit, the investigator evaluates efficacy, safety and tolerability of the investigated treatment. Patients will continue to take bisoprolol 5 mg (7.5 mg) until next visit V2. If BP control is insufficient with bisoprolol 7.5 mg QD, the investigator adds perindopril 10 mg QD.

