#### **5.5 Analysis of compliance**

At every visit, starting with visit V2, the dispensed and returned investigated product is counted, and the patient compliance is assessed. The investigator or his/her authorized representative will count the number of dispensed and returned tablets and document it in the accountability form and CRF. Additionally, date of the first and last product administration, and deviations in the product dosing regimen within the last intervisit interval (if any) will be documented in CRF.

In case of low patient compliance with the investigated treatment (the patient took <80 tablets within the intervisit interval), the patient will be withdrawn from the study.

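### Section 5.5 withdraws patients below 80 tablets per interval where section 4.5 says below 80%; no fixed count can stand in for 80% here, and the one-tablet dosing wording leaves the tablets due unclear

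*Combined protocol and SAP*

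**What the plan says.** **Compliance threshold.** Section 4.5 lists, among the grounds for withdrawal, "Low treatment compliance (<80" per cent. Section 5.5 counts tablets at every visit from V2 and gives the rule as "the patient took <80 tablets within the intervisit interval), the patient will be withdrawn from the study".

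**Visit spacing.** V2, V3 and V4 fall on days 56, 168 and 336 after enrolment, each ±5 days (sections 3.6.2, 3.6.4 and 3.6.5).

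**Tablets.** Moxonidine starts at 0.4 mg and may rise to 0.6 mg from week 2. Strengths of 0.4 mg and 0.2 mg are listed in 3.8.1, and the V1 supply is "moxonidine 0.4 mg in the amount required for 56 days of treatment plus 7 extra days and additionally moxonidine 0.2 mg" for 42 days in case of titration. Bisoprolol starts at 5 mg, and section 5.1 says "If BP control is insufficient, the investigator will increase bisoprolol dose to 7.5 mg QD". The only strength described is in 3.8.2: "One tablet contains bisoprolol hemifumarate and bisoprolol fumarate (2: 1) as active substances 5 mg".

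**Dosing instruction.** At V2, and again at V3: "The patient will be instructed to start taking the provided product the next day morning, 1 tablet per day". Section 5.1 has, for both arms: "One tablet of the investigated product should be taken daily, in the morning, regardless of meals".

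**Analysis.** Sections 6 and 10.3 place the efficacy analysis in the per-protocol set. Section 10.2 says that non-completers are added by last observation carried forward. The ITT set requires data from V3 or V4.

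**The concern.** The two sections give the same withdrawal ground in different units, and the units cannot be reconciled. A percentage scales with the length of the interval and the number of tablets a day. A fixed count does not, so it is too strict in the short first interval and too lenient in the long later ones.

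At stake is who is analysed. A patient withdrawn for low compliance has not completed per protocol and leaves the efficacy set. CTX is scheduled at V1, V3 and V4 only (section 3.4). A patient withdrawn at V2 therefore has no post-baseline CTX, and falls outside the ITT set too, unless she attends for the early final-visit procedures that section 4.6 requests where possible.

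The one-tablet wording bears on the same rule. Compliance is a tablet count, so the number of tablets due at each dose must be known. For bisoprolol 7.5 mg it is not stated.

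**Working it through.** The plan gives no figure of its own to reproduce. The check converts the 80-tablet rule into a percentage for each interval and dose.

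**Inputs.** Nominal intervals: 56 days; 168 − 56 = 112 days; 336 − 168 = 168 days. With ±5 days at each visit: 51–61, 102–122 and 158–178 days. Tablets a day: 1 at the starting dose of either drug; 2 for moxonidine 0.6 mg (0.4 + 0.2). For bisoprolol 7.5 mg, 7.5/5 = 1.5 is an assumption, because the documents do not say. Only moxonidine or bisoprolol tablets are counted.

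**Formulas.** Tablets due = days × tablets a day. Implied cut-off = 80 / tablets due.

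**V1–V2, perfect intake**

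- Untitrated: 56 × 1 = 56 tablets (51–61), always below 80. The whole 0.4 mg moxonidine supply is 56 + 7 = 63, also below 80.
- Moxonidine raised at day 14: 14 + 42 × 2 = 98, kept.
- Bisoprolol raised at day 14, at 1.5 tablets: 14 + 42 × 1.5 = 77 on day 56, withdrawn. The count reaches 14 + 44 × 1.5 = 80 on day 58 and 14 + 47 × 1.5 = 84.5 on day 61, so the outcome turns on the visit day. If 7.5 mg were one tablet of another strength, 56 would be due; if two tablets, 98.

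**After V2: patients are flagged only below this share of the tablets due**

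| Dose | V2–V3, nominal (window) | V3–V4, nominal (window) |
|---|---|---|
| One tablet a day | 80/112 = 71% (66–78%) | 80/168 = 48% (45–51%) |
| Moxonidine 0.6 mg | 80/224 = 36% (33–39%) | 80/336 = 24% (22–25%) |
| Bisoprolol 7.5 mg, 1.5 tablets | 80/168 = 48% (44–52%) | 80/252 = 32% (30–34%) |

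**What section 4.5 would require at one tablet a day:** 0.8 × 56 = 44.8 tablets, 0.8 × 112 = 89.6 and 0.8 × 168 = 134.4. A count of 80 lies well above the first, somewhat below the second and far below the third.

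**The case against.** The best defence is that the count is an obvious slip. Section 4.5 states the intended rule. V2 is the first compliance check, and there the literal rule would remove every untitrated patient. A site would notice, and would hardly return to the literal count at V3 and V4. At the short end of the V2–V3 window the one-tablet cut-off is 78%, close to 80%. This stands as a reason not to expect mass withdrawal at V2. It does not make the text right: the correction is left to whoever spots it, and the rule helps decide membership of the efficacy set.

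A reader might also infer that titrated patients would be under-dosed, since one tablet gives 0.4/0.6 or 5/7.5, that is 67% of the ordered dose. The documents do not support expecting this. The text beside the one-tablet sentence orders titration where the target is missed and otherwise says "If the target BP has been reached, the patient continues with the current treatment until the next visit". The extra 0.2 mg tablets are supplied for titration, and section 5.6 provides for the amount needed. In 5.1 the sentence follows the starting-dose prescription and precedes the titration steps, although nearby wording about the whole study leaves it loose. The missing bisoprolol make-up is an omission, not a contradiction.

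A reader might see a further conflict in 4.5 saying that patients may be withdrawn while 5.5 says they will be. The former introduces a list that includes death and withdrawal of consent, so it is weak evidence of intended discretion.

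**Conclusion.** The concern holds for the compliance threshold. Sections 4.5 and 5.5 conflict, and the count in 5.5 is wrong as a withdrawal rule. Taken literally it fails every fully compliant untitrated patient at V2 (51 to 61 tablets due). After V2 it flags one-tablet patients only below about 71% and then 48%, and moxonidine 0.6 mg patients below about 36% and then 24%. It can also treat equal adherence differently by arm: on day 56, after titration at week 2, perfect intake is 98 tablets on moxonidine and 77 on bisoprolol. That comparison rests on 7.5 mg being one and a half 5 mg tablets.

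A reader might infer that the CTX comparison is biased towards one drug. The documents do not support that: they give neither the share titrated nor the share non-compliant, and the literal rule may never be applied. No size or direction of bias is claimed. How far withdrawn patients would re-enter is also unclear, because section 10.2 provides for carrying the last observation forward without reconciling this with a per-protocol efficacy set.

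The one-tablet wording and the unstated bisoprolol make-up are minor points. They matter here mainly because they leave the denominator of an 80% rule undefined for titrated bisoprolol.

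**What to change.** 1. In section 5.5, replace the tablet count with: *less than 80% of the tablets due at the patient's prescribed dose in that interval*. This matches section 4.5.
2. As a minor clean-up in 3.6.4, 3.6.5 and 5.1, replace the one-tablet wording with: *the tablets that make up the prescribed dose*. State that moxonidine 0.6 mg is one 0.4 mg plus one 0.2 mg tablet, and state how bisoprolol 7.5 mg is made up (one and a half 5 mg tablets, if the product may be split).

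The cost is protocol and patient-instruction wording, with no change to visits, sample size or analysis method. If the bisoprolol tablet may not be split, another strength would be needed; that is a separate supply decision.

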### **3.6.5 Visit 3 (V3)**

The investigator will document the disease history since the last visit, including all adverse events, changes in concomitant treatment, changes in concomitant medications doses, if any.

The investigator will analyze the effectiveness of the therapy according to the patient's BP self-monitoring diary data.

The investigator measures BP and HR according to the ESH/ESC recommendations that are listed in Appendix 1. Blood pressure and heart rate are measured in a sitting position after 5 minutes of rest. **Two** measurements are done, the average value of the measurements is documented. BP is measured on the same arm during the entire study.

Fasting blood sampling will be carried out for the following tests: BMP (potassium, sodium, creatinine, total calcium, inorganic phosphorus, ALT, AST), hormonal test (PTH) and bone metabolism tests, including osteocalcin, Ctx, OPG, RANKL.

The investigator evaluates response to the treatment (target BP reaching), documents it in source documents and decides on further treatment of the patient. If target BP has not been reached, the patient's investigated product dose is titrated according to the study design. If the target BP has been reached, the patient continues with the current treatment until the next visit.

The investigator analyzes the patient's compliance based on the number of returned tablets. The investigator will provide the patient with the investigated medications and invite the patient to the next visit (visit V4) scheduled for week 48 after the enrollment visit (336 days  $\pm$  5 days after the enrollment visit); the patient will be asked to return the investigated medication blisters (empty, started and not started blisters). The patient will be instructed to start taking the provided product the next day morning, 1 tablet per day. The patient will be instructed to report any adverse events (if applicable) to the investigator.

### **3.6.6 Final visit (V4)**

The investigator will document the disease history since the last visit, including all adverse events, changes in concomitant treatment, changes in concomitant medications doses, if any.

The investigator will analyze the effectiveness of the therapy according to the patient's BP self-monitoring diary data.

The investigator measures BP and HR according to the ESH/ESC recommendations that are listed in Appendix 1. Blood pressure and heart rate are measured in a sitting position after 5 minutes of rest. Two measurements are done; the average value of the measurements is documented. BP is measured on the same arm during the entire study. Full physical examination is not required.

Patient's biochemical blood analysis (total calcium, inorganic phosphorus) is performed. Blood is sampled to investigate bone metabolism: osteocalcin, Ctx, OPG, RANKL.

Blood is sampled to determine telomerase activity.

Dual energy X-ray absorptiometry to determine BMD and detect osteopenia is performed.

Applanation tonometry method is used to measure changes in patient's PWV; duplex ultrasonography of extracranial brachiocephalic arteries is employed to evaluate IMT and subclinical atherosclerosis.

The investigator evaluates the response to the treatment (target BP reaching) and documents it in the source documents, as well as estimates patient compliance based on amount of the returned investigated product.

After successful completion of visit V4 procedures, the patient completes her participation in the study. The investigated product is discontinued; further treatment is carried out according to the attending physician advice.

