## **3. PROGRAM PLAN AND PROCEDURES**

### **3.1 General design**

This is explorative, randomized, open-label, interventional, comparative clinical trial.

Study population is postmenopausal women with essential hypertension and osteopenia. The study will enroll 114 patients after screening (it is expected that 300 patients will need to be screened in order to reach this enrollment goal).

After the informed consent signing, the patient's participation in the study will include the period before the studied product administration, the treatment period and the final visit.

Patients will be randomized to one of two groups: moxonidine group or bisoprolol group.

According to the study protocol, patients randomization to the control and investigated groups will be carried out using a simple envelopes method and, therefore, it is assumed that the control and the investigated groups will be matched by the basic measured parameters; the number of subjects in the main and control groups is planned to be equal.

The study endpoints are measured prior to the studied product initiation (V1) and after completion of 48-week treatment with the investigated product (V4).

The period prior to the studied treatment initiation is designed to assess the patient meeting inclusion criteria and to carry out 7-10-day washout period in patients with previous antihypertensive therapy. The planned duration of the period before the treatment initiation does not exceed 14 days after the signing of the informed consent form by the patient.

Then, at the enrollment visit during the treatment period, the investigator will assess the patient meeting the inclusion criteria. If the inclusion criteria are met, the patient will be enrolled in the study. The baseline condition data will be obtained from the patient, and then the patient will be randomized to one of the two treatment groups (moxonidine or bisoprolol). The treatment period involves the enrollment visit (V1), and 3 more visits.

The final visit 4 is carried out at week 48 after the enrollment visit, the patient then completes the study.

The patients' treatment includes gradual titration of the studied products doses.

Group 1 will receive moxonidine with the dose titrated to a maximum, and then, if necessary, the patient will be shifted to the combination therapy (Step 2 – adding an ACE inhibitor)

[figure not shown]

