### 3.2 Patients randomization and identification

The study participants are randomized using a simple envelopes method. An independent person will generate a random table for 114 records in which 57 will be marked as “M” and 57 will be marked as “B”. According this computer based randomization table cards with letter “B” or “M” will be sealed in 114 numbered envelopes. The randomization table will also be sealed in a separated envelope. The numbered envelopes will be sent to Principal Investigator. The envelope with randomization table will be stored in the Sponsor file.

Each patient is assigned with a special identification code that is only used in the program. The code is assigned to a patient after enrollment and includes the health care facility code and the patient number.

According to the protocol, decoding keys for the identification codes are not provided. Persons authorized by the Sponsor, health care or other regulatory authorities may inspect any program data available to the investigator.

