### **3.6.2 Enrollment visit (V1)**

Enrollment visit is conducted no later than 14 days after signing the informed consent form by the patient.

The investigator documents all significant changes in the history of hypertension and concomitant treatment (including fast acting antihypertensives to relieve a hypertension episode that may be administered during the washout period); the investigator identifies and documents adverse events associated with the protocol procedures, if any, starting from the date of the informed consent signing.

The investigator conducts a physical examination of the patient by organs and organ systems that must include measurement of heart rate, systolic and diastolic blood pressure according to ESH/ESC recommendations that are listed in Appendix 1 [17]. Blood pressure and heart rate are measured in a sitting position after 5 minutes of rest on the arm with the highest BP during screening. Three measurements are done; the average value of the measurements is documented. The investigator assesses hypertension severity and grade according to the ESH/ESC recommendations that are listed in Appendix 2.

Applanation tonometry method is used to measure changes in patient's PWV; duplex ultrasonography of extracranial brachiocephalic arteries is employed to evaluate IMT and subclinical atherosclerosis.

Blood is sampled to investigate bone metabolism: osteocalcin, Ctx, OPG, RANKL.

Blood is sampled to determine telomerase activity.

The investigator may enroll the patient in the study and start the investigated treatment only if the patient meets all the screening criteria to start the treatment.

The investigator randomizes patients to one of two treatment groups by means of the simple envelopes method.

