#### **Secondary Endpoints:**

- To assess mean values of osteocalcin at visit 4 versus baseline level (visit 1) and to compare the values between the groups
- To assess mean values of the receptor activator of nuclear factor kappa-B ligand (RANKL) at visit 4 versus baseline level (visit 1) and to compare the values between the groups
- To assess mean values of BMD at visit 4 versus baseline level (visit 1) using control dual-energy X-ray absorptiometry and to compare the results between the groups
- To assess mean telomerase activity at visit 4 versus baseline level (visit 1) and to compare the values between the groups
- To assess mean pulse wave velocity (PWV) at visit 4 versus baseline level (visit 1) and to compare the values between the groups
- To assess mean intima-media thickness (IMT) at visit 4 versus baseline level (visit 1) and to compare the values between the groups
- To estimate the proportion (%) of patients who achieved target blood pressure <140/90 mmHg at the visit 2 (Week 8), 3 (Week 24) and 4(Week 48) and according to the patient's diary.

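### In this open-label trial nothing keeps the arm from those who take or read PWV, IMT and DXA at V4, so these secondary comparisons are open to a reading bias that coded requests would reduce at little cost

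*Combined protocol and SAP*

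**What the plan says.** Section 3.1 sets the design: "This is explorative, randomized, open-label, interventional, comparative clinical trial". Section 3.6.2 says who allocates: "The investigator randomizes patients to one of two treatment groups by means of the simple envelopes method". The investigator therefore knows each patient's arm from V1 onward.

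The three measurements at V4 are described in section 3.6.6 without an agent. For vascular stiffness: "Applanation tonometry method is used to measure changes in patient's PWV". For bone density: "Dual energy X-ray absorptiometry to determine BMD and detect osteopenia is performed". For the carotid measurement, 3.6.6 uses the same words as 3.6.2: "duplex ultrasonography of extracranial brachiocephalic arteries is employed to evaluate IMT and subclinical atherosclerosis". Section 3.7, which describes individual procedures, covers laboratory testing only.

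On timing, section 3.1 says: "The baseline condition data will be obtained from the patient, and then the patient will be randomized to one of the two treatment groups". The schedule in section 3.4 places densitometry at V0 and V4, and PWV and IMT at V1 and V4.

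Sections 3.10 and 6.2 list BMD, PWV and IMT among seven secondary endpoints, each compared between groups. The primary endpoint is the change in CTX.

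On the identifier, section 3.2 says: "The code is assigned to a patient after enrollment and includes the health care facility code and the patient number". The code has no treatment element. The protocol does not say that scans, recordings or request forms are labelled with it.

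**The concern.** Tonometry depends on how the operator holds the probe and which recordings are accepted. Ultrasound IMT depends on the segment and boundary chosen. DXA depends on positioning and region placement, probably to a lesser degree. These are general measurement judgements; the protocol does not make them. When the person making such choices may know the treatment, expectation can move the reading, and a confidence interval does not show a shift of that kind.

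PWV and IMT are the only vascular measures listed as endpoints for the secondary objective on cellular and vascular aging. BMD is the only density measure for the objective on bone metabolism and density. Section 10.5 gives publication as the focus of the study, and unmasked reading of these measures is a foreseeable criticism. It is easy to reduce before V4, and for live measurements it cannot be repaired afterwards.

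**Working it through.** **1. Which readings can be influenced.** The order of events follows from sections 3.1, 3.4, 3.6.1 and 3.6.2:

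| Measure | Baseline | Arm known at baseline? | Follow-up | Arm known at follow-up? |
|---|---|---|---|---|
| DXA (BMD) | V0 | No, before randomization | V4 | Not stated |
| PWV | V1 | No, before randomization | V4 | Not stated |
| IMT | V1 | No, before randomization | V4 | Not stated |

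Only V4 is open to arm-aware reading.

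**2. How a V4 shift enters the result.** Let d(M) and d(B) be the average reading errors at V4 caused by knowing the arm, for moxonidine and bisoprolol. The expected difference in change between arms is the true difference plus d(M) − d(B). Nothing at baseline cancels this term. A constant shift leaves the SD unchanged, so the interval keeps its width around a displaced centre.

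**3. Is there a figure in the plan to reproduce?** No. Section 10.5 states that no formal sample size calculation was done, and the plan gives no SD, effect size or power. Section 3.2 fixes the allocation list at 57 + 57 = 114. Section 10.5 gives a minimum enrolment of 100, which is 50 per arm. Section 10.1 sets two-sided tests at 0.05.

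**4. Illustration of scale.** Assume no true effect, a two-sample t-test on the change score (the plan names no test), and a systematic difference b = d(M) − d(B) in SD units of the change score. The value of b is an assumption.

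Noncentrality = b × √(n/2), degrees of freedom = 2n − 2.

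- n = 57: √28.5 = 5.339, df = 112, critical t = 1.981. For b = 0.1, 0.2 and 0.3 the noncentrality is 0.534, 1.068 and 1.602.
- n = 50: √25 = 5, df = 98, critical t = 1.984. For b = 0.1, 0.2 and 0.3 the noncentrality is 0.5, 1.0 and 1.5.

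False-positive rate from the noncentral t distribution:

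| b (SD of change) | 57 per arm | 50 per arm |
|---|---|---|
| 0 | 5.0% | 5.0% |
| 0.1 | 8.3% | 7.9% |
| 0.2 | 18.5% | 16.8% |
| 0.3 | 35.5% | 31.8% |

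By the normal approximation, a shift of about 0.12 SD at 57 per arm doubles the rate to 10%. For comparison, the true difference detectable with 80% power at 57 per arm is (1.960 + 0.842) × √(2/57) ≈ 0.52 SD.

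Fifty-seven per arm is an upper limit, because section 10.3 analyses efficacy in patients who completed according to protocol.

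**5. What the code can and cannot do.** It holds a facility code and a patient number, so a V4 request or stored image labelled with it does not disclose the arm. It is assigned after enrollment, so it does not exist at the V0 DXA, but it is available by V4. It can mask the reading of a stored image. It cannot mask a live session with a patient who knows her drug.

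**The case against.** The strongest reply is that silence is not exposure. The protocol names no operator. If separate staff take these measurements, nothing shows that they are told the arm. That stands, so the finding is a missing safeguard and not a demonstrated bias.

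The direction of any expectation is also unsettled. Section 1.1 presents moxonidine as promising for vascular aging, but it also lists beta-blockers among drugs that reduce arterial stiffness and reports favourable bone data for them.

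Section 10.3 says that efficacy results will be presented descriptively, which weakens the false-positive framing. It does not remove the point, because a reading shift displaces the estimated difference whether or not a test is applied.

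A reader might also infer several stronger things that the documents do not support:

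- **That masking would be free.** The documents give no staffing or cost information, and a coded request form is needed.
- **That baseline procedures also need changing.** The arm does not exist at V0, or at V1 when PWV and IMT are taken.
- **That half of all eight endpoints are affected, counting clinic blood pressure.** Blood pressure is a separate case. Section 3.6.6 says that the investigator, who knows the arm, measures it, and the change proposed here does not alter that.
- **That stored images can simply be re-read.** No section says that images are kept.

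**Conclusion.** The point holds in a narrow form. PWV, IMT and BMD are between-arm secondary endpoints in an open-label trial, and the plan does not keep the arm from those who acquire or read them at V4. Arm-aware reading could therefore bias the V4-minus-baseline differences.

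The size of any bias is unknown. The rates of 8.3%, 18.5% and 35.5% rest on assumed shifts of 0.1, 0.2 and 0.3 SD of the change score, on a t-test that the plan does not name, and on the full 57 per arm. They show that a shift well below the detectable difference would matter, not that one is present.

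It would be wrong to infer that the main result is compromised: CTX is a blood assay and is little exposed. The study also calls itself explorative. This is a worthwhile, cheap improvement of low severity. The absence of masking is judged on the text supplied, from which some pages were removed.

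**What to change.** Add to section 3.6.6 (V4) only: *Requests for PWV, IMT and DXA carry only the patient code and visit; operators are not told the treatment and patients are asked not to discuss it; where IMT and DXA images are stored, the existing reader measures them under the code alone.*

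No added reader is needed. Where the treating investigator is the only available PWV operator, report that reading as unmasked. Section 3.6.2 needs no change.

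The cost is protocol wording and a coded request form. Masking of live measurements will be only partial, because the patient knows her drug and may mention it. The open-label design, sample size, visits and treatment are unaffected.
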